## J. Hazards and Discomforts

1. **The risks and discomforts of frequent phlebotomy.** To document stable levels of biochemical and serologic markers of chronic hepatitis and to monitor the effects and toxicities of the combination of tenofovir and FTC, frequent blood sampling will be required. Patients will have between 11 and 12 venipunctures during the first 48 weeks of the study and 4 to 6 each year thereafter. Each venipuncture will be for approximately 20 to 75 cc of blood. The total amount of blood drawn during an 8 week period will not exceed 10.5 ml/Kg or 550 mls, whichever is smaller.
2. **The risks and discomforts of HIV testing.** Patients will have blood tested for anti-HIV at entry. Mention of anti-HIV is made in the consent form which includes the exact language used in the standard consent form used for anti-HIV testing at the Clinical Center. It is important to test for HIV infection as both tenofovir and emtricitabine have activity against HIV and a treatment regimen using only two drugs against HIV would not be considered standard of care.
3. **The risks and discomfort of percutaneous liver biopsy.** Patients will undergo up to three liver biopsies in this protocol namely: one before therapy, a second at 48 weeks, and a third at 192 weeks. Patients will not have to undergo the initial liver biopsy if they had a biopsy within the previous 2 years that is adequate and available for analysis. In addition, patients with inadequate platelet counts ( $<70,000/\text{mm}^3$ ) or coagulation parameters (prothrombin time  $> 15$  seconds, INR $>1.7$ ) will not undergo liver biopsy as a part of this protocol. Patients requiring liver biopsy will be admitted to the Clinical Center for two days for this procedure and other blood testing. The major side effects of liver biopsy are pain, bacteremia, puncture of another organ and bleeding. Local pain and discomfort at the liver biopsy site occurs in about 20% of persons undergoing percutaneous liver biopsy. This is transient (lasting one to twelve hours) and is usually mild, rarely requiring analgesics. Bacteremia occurs in 1-2% of persons undergoing liver biopsy. In the absence of bile duct obstruction, this is

almost always self-limited and is rarely symptomatic. Significant bleeding after liver biopsy is the most serious side effect of this procedure. In the absence of a blood coagulation defect or hepatic malignancy, significant bleeding is rare, occurring in less than one in a thousand cases of liver biopsy. Death due to bleeding after liver biopsy has been reported in less than 1/10,000 cases. At the NIH Clinical Center, the Liver Diseases Branch has performed approximately 150 liver biopsies each year for the last 20 years. During this time, only two patients died as a complication of biopsy. One of these patients had cirrhosis and advanced hepatocellular carcinoma and the second had severe coagulation disorders. Both bled from the liver biopsy site and died after surgical attempts to stop the bleeding were unsuccessful.

4. **The risks and hazards of tenofovir therapy.** See section G.
5. **The risks and hazards of tenofovir and emtricitabine combination therapy.** See section G.

#### **L. Data and Safety Monitoring**

The adequacy of data acquisition and storage and the monitoring of safety in this trial will be done by the principal investigator in collaboration with the associate investigators. Data and safety are reviewed weekly in clinical research rounds by the Liver Diseases Branch, NIDDK. These rounds are separate from regular clinical rounds and consist of review of all study patients including flow sheets of major safety and efficacy measurements without knowledge of which therapy is used. Monitoring of this study will also be conducted by the statistical department of NIDDK who will have knowledge of the patient allocation. Reports of serious adverse events are made to the Clinical Director NIDDK, the IRB, study monitor and the FDA.

#### **M. Adverse Event Reporting**

Adverse events, protocol deviations, unanticipated problems (UP), Unanticipated Adverse Device Effects (UADEs), serious adverse events, sponsor and serious, are defined as described in NIH HRPP SOP 16 (“Reporting Requirements for Unanticipated Problems, Adverse Events and Protocol Deviations.”). All adverse events at least possibly related to the patient’s participation in the research protocol, including those observed by or reported to the research team, will be recorded. Serious unanticipated problems and serious protocol deviations will be reported to the IRB and CD as soon as possible but not more than 7 days after the PI first learns of the event. Not serious unanticipated problems will be reported to the IRB and CD as soon as possible but not more than 14 days after the PI first learns of the event.

Non-serious protocol deviations will only be reported to the IRB (within 14 days after the PI first learns of the event) if they represent a departure from NIH policies for the conduct of human subjects research, adversely affect the health care of the subject(s) or compromise the interpretation or integrity of the research. Non-serious protocol

deviations that result from normal subject scheduling variations or technical issues associated with sampling that does not impact the health of the subject or the interpretation of the study data will not be reported.

All serious adverse events that are assessed as possibly, probably or definitely related to tenofovir or tenofovir plus emtricitabine will be reported to the FDA and Gilead within 15 days by submission of a serious adverse event form and a written report for events occurring within this protocol. Adverse events that are expected as a part of treatment or procedures outlined in the protocol will not be reported unless they occur at a rate or severity greater than known to occur in patients undergoing the treatment or procedures. If AEs associated with the treatment and procedures in the study occur at a rate or severity greater than known to occur, they will be reclassified as a UP and reported as such. AEs with known relation to the natural history of chronic hepatitis B or to other pre-existing conditions will not be reported unless they occur at a rate or severity greater than known to occur in patients with hepatitis B or the subject's other pre-existing conditions. AEs that are unrelated to the research will not be reported. The PI is responsible for summarizing all reportable serious adverse events and adverse events at the time of Continuing Review. Deaths and life-threatening events will be reported to the Clinical Director and IRB within 7 days after the PI first learns of the event. Any pregnancies that occur during the study and of the outcome of those pregnancies with relevant information will be reported to Gilead on a timely basis.

Any information in the literature, or that has evolved from similar research, and that might affect the IRB's analysis of risk/benefit for the protocol will be reported to the IRB at the time of Continuing Review. If such information is obtained before the time of continuing review, it should be reported to the IRB at the time that it becomes known, and summarized at the time of continuing review.

Study procedures will be subject to audits and/or monitoring visits to ensure compliance with the protocol and applicable regulatory requirements consistent with the NIDDK quality assurance program plan. Audit and/or monitoring visit results will be reported to the Principal Investigator for further reporting as appropriate. Study documents and pertinent hospital or clinical records will be reviewed to verify that the conduct of the study is consistent with the protocol plan.

## **N. Enrollment of Children, Women and Minority Individuals**

The current protocol excludes children (age limit > 18 years) as tenofovir has not been used in children for the treatment of chronic hepatitis B. Currently lamivudine is approved for use in children. Chronic hepatitis B is rare in children in the U.S. and the implications of long-term therapy are great.

Chronic hepatitis B is much more common among men than women. We expect to include women in the proportions that occur in this disease. Thus, we expect 10-20% of patients to be women. The exclusion of women interested in getting pregnant or who are not able to practice adequate birth control would be the only possible bias introduced in attaining adequate representation of women in this study.

The distribution of minority individuals in recent studies of nucleoside therapy of hepatitis B at the NIH Clinical Center has been reported yearly to the NIDDK IRB. In our study of adefovir and lamivudine (01-DK-0246), 62% of 39 enrolled patients were minority individuals, including 46% Asian-Americans, 13% African-Americans and 3% Hispanic Whites. Chronic hepatitis B is far more common among Asian Americans (2 to 10% of adults) than African Americans (1-2%) and Caucasians (~0.5%) and we expect that at least one-third of patients enrolled in this study will be Asian-Americans. There is no reason to suspect that response rates are different in different racial or ethnic groups.

#### **O. Research Use, Storage and Disposition of Human Samples and Data:**

Patients will have serum stored from selected time points during this study. These specimens will be used for repeat virological testing and special tests as needed (such as for viral levels, HBV genotype or serotype, HBV DNA sequence or testing for serum levels of cytokines or interferon induced genes). Samples may be used to assess factors associated with response or non-response to antiviral therapy. Liver biopsy tissue may be stored if a biopsy is done before therapy and if residual tissue is available after routine samples are taken for routine histological staining and evaluation. These samples will be tested in the Liver Diseases Branch or the routine clinical and surgical pathology services of the Clinical Center. Stored serum will be used to perform in vitro antiviral susceptibility and cross resistance testing. Gilead Sciences will conduct these assays and serum samples will not contain any patient identifiers. Samples will be sent as soon as virologic breakthrough is identified and Gilead will have one year after receipt of the sample in which to provide LDB, NIDDK with the results. Research records and data as well as liver biopsy slides, biopsy reports, liver tissue and sera with the patient's name and a unique identifier will be stored indefinitely in our locked offices and freezers, the medical record department and the pathology department. These materials will be protected and tracked by standard operating procedures in the medical record and pathology departments as well as a compulsive filing system in our locked offices and freezers. There will be redundant storage of clinical information in the medical record department and our offices. Likewise, there will be redundant storage of biopsy information and materials in the pathology department and our offices. This should minimize the risk of loss or destruction of information and specimens. If that were to occur we would report it to the IRB. We do not plan to destroy this personal medical information or the liver biopsy specimens or research subject sera after completion of the

study because it may be critically important for physicians (here or elsewhere) to have access them when caring for these patients in the future.

## **P. Consent process**

Written informed consent will be obtained from the participant prior to any screening visits, study procedures or treatments. The Principal Investigator or other designated qualified protocol investigators (listed on the protocol's face page) will explain the study in language understandable to the subject. Potential study subjects will be informed of study rationale, design, participation burden, risks, benefits and side effects of therapy during routine LDB clinic visits and will have an opportunity to ask questions about the proposed study. They will be provided a copy of the study consent form to take home and review in more detail. Sufficient time and opportunity will be given for discussion of the research as well as to answer any questions they may have, taking care to minimize or eliminate the perception of coercion or undue influence. The participant and the investigator will sign the current IRB-approved informed consent document. A witness will also sign the consent document to attest only to the validity of the signature of the subject, not the validity or quality of the consent. A copy of the consent will be given to the subject for future reference. The signed documents will be sent to the Medical Records Department for placement in the subject's permanent CC medical record. The consent process will additionally be documented in the medical record.

If a subject indicates a desire to participate in the research study, he/she will have all screening laboratories, radiologic imaging and if necessary, liver biopsy, performed through our natural history protocol 91-DK-0214. Hepatitis B can be a very dynamic disease and liver pathology can change rapidly as opposed to the scenario with hepatitis C. In contrast to other chronic liver diseases a liver biopsy is very helpful and in some cases essential to manage patients with chronic hepatitis B. How often one should perform a follow-up biopsy is open to debate and is influenced by many factors. For clinical investigation the ideal duration to perform a baseline liver biopsy would be within one year prior to enrollment, however a period of 2 years seems a reasonable compromise without being arbitrary. In our experience 2 years provides enough time for clinically significant changes to be observed without subjecting patients to unnecessary risk. We believe that it is medically indicated for every patient with chronic hepatitis B to undergo a liver biopsy before embarking on therapy that may last more than a decade. Potential study subjects who meet study inclusion and exclusion criteria will sign the consent form on day 0 of therapy, prior to randomization.

### **P.2 Short Form Consent**

We do not plan to enroll non-English speaking subjects; however they are not excluded from participation either. Should a non-English speaking subject be enrolled, IRB approval will be obtained to use the short form process in the absence of a fully translated consent document. Requests for IRB approval will be obtained prior to implementing the short form consent process. The short form consent process will be in compliance with SOP 12.9.1 of 45 CFR 46.117(b)(2).

Creatinine Clearance		X								X		X
Ultrasound‡		X								X		X
Liver biopsy		X								X		X
Alpha fetoprotein‡		X								X		X
Immunologic tests		X		X	X		X			X		
Fibroscan‡		X								X		X
Bone mineral density		X								X		X
FTCvsPlacebo/Tenofovir		X	X	X	X	X	X	X	X	X	X	X

\* Pre is the initial evaluation which will be an outpatient clinic visit for those who do not require a pretreatment biopsy and a clinical center admission for those who require a pretreatment liver biopsy.

† Routine bloods include CBC, chemistry-20 panel, serum lactic acid and HBV DNA by quantitative PCR.

‡ Urine tests include standard urine analysis and spot urine protein/creatinine ratio and a pregnancy test for women of child bearing potential.

¶ Extended tests include: INR, alphafetoprotein, HBsAg, anti-HBs, HBeAg and anti-HBe and are measured every 12 weeks.

‡ Ultrasound and fibroscan will be measured every 48 weeks.

**Appendix B.**

Table 1 Common Toxicity Criteria

Adverse event	Grade				
	0	1	2	3	4
Nausea	None	Able to eat	Oral intake significantly decreased	No significant intake, requiring IV fluids	-
Diarrhea patients without colostomy:	none	increase of <4 stools/day over pre-treatment	increase of 4-6 stools/day, or nocturnal stools	increase of 7 stools/day or incontinence ; or need for parenteral support for dehydration	Physiologic consequences requiring intensive care; or hemodynamic collapse
Fatigue (lethargy, malaise, asthenia)	None	increased fatigue over baseline, but not altering normal activities	moderate (e.g., decrease in performance status by 1 ECOG level or 20% Karnofsky or Lansky) or causing difficulty performing some activities	severe (e.g., decrease in performance status by 2 ECOG levels or 40% Karnofsky or Lansky) or loss of ability to perform some activities	bedridden or disabling
Myalgia (muscle pain)	none	mild pain not interfering with function	moderate pain: pain or analgesics interfering with function, but not interfering with activities of daily living	severe pain: pain or analgesics severely interfering with activities of daily living	disabling
Confusion	normal	Confusion or	Confusion or	Confusion or delirium	Harmful to others or

		disorientation or attention deficit of brief duration; resolves spontaneously with no sequelae	disorientation or attention deficit interfering with function but not interfering with activities of daily living	interfering with activities of daily living	self; requiring hospitalization
Mood alteration-anxiety, agitation	normal	mild mood alteration not interfering with function	moderate mood alteration interfering with function, but not interfering with activities of daily living	severe mood alteration interfering with activities of daily living	suicidal ideation or danger to self
Mood alteration-	normal	depression mild mood alteration not interfering with function	moderate mood alteration interfering with function, but not interfering with activities of daily living	severe mood alteration interfering with activities of daily living	suicidal ideation or danger to self
Mood alteration-euphoria	normal	mild mood alteration not interfering with function	moderate mood alteration interfering with function, but not interfering with activities of daily living	severe mood alteration interfering with activities of daily living	danger to self
Vision-	normal	-	symptomatic	symptomatic	-

blurred vision			and interfering with function, but not interfering with activities of daily living	and interfering with activities of daily living	
Vision-double vision (diplopia)	normal	-	symptomatic and interfering with function, but not interfering with activities of daily living	symptomatic and interfering with activities of daily living	-
Inner ear/hearing	normal	hearing loss on audiometry only	tinnitus or hearing loss, not requiring hearing aid or treatment	tinnitus or hearing loss, correctable with hearing aid or treatment	severe unilateral or bilateral hearing loss (deafness), not correctable
Fever (in the absence of neutropenia, where neutropenia is defined as AGC <1.0 x 10  /L)	none	38.0 - 39.0°C (100.4-102.2°F)	39.1 - 40.0°C (102.3 - 104.0°F)	>40.0°C (>104.0°F) for<24hrs	>40.0°C (>104.0°F) for>24hrs
Leukocytes (total WBC)	WNL	<LLN - 3.0 x 10  /L<LLN 3000/mm 	2.0 - <3.0 x 10  /L 2000 - <3000/mm 	1.0 - <2.0 x 10  /L 1000 - <2000/mm 	<1.0 x 10  /L<1000/m m 
Neutrophils/granulocytes (ANC/AGC)	WNL	1.5 - <2.0 x 10  /L 1500 - <2000/mm 	1.0 - <1.5 x 10  /L 1000 - <1500/mm 	0.5 - <1.0 x 10  /L 500 - <1000/mm 	<0.5 x 10  /L<500/mm 
Hemoglobin	(Hgb) WNL	<LLN - 10.0 g/dL	8.0 - <10.0 g/dL	6.5 - <8.0 g/dL	<6.5 g/dL
Platelets	WNL	<LLN - 75.0	50.0 -	10.0 -	<10.0 x 10 

		$\times 10^9$ /L < LLN - 75,000/mm 	<75.0 $\times 10^9$ /L 50,000 - <75,000/mm 	<50.0 $\times 10^9$ /L 10,000 - <50,000/mm 	/L <10,000/ mm 
Alkaline phosphatase	WNL	>ULN - 2.5X ULN	>2.5 - 5.0 X ULN	>5.0 - 20.0 x ULN	>20.0 X ULN
SGPT (ALT) (serum glutamic pyruvic transaminase)	WNL	>ULN - 2.5X ULN	>2.5 - 5.0 X ULN	>5.0 - 20.0 x ULN	>20.0 X ULN
SGOT (AST) (serum glutamic oxaloacetic transaminase)	WNL	>ULN - 2.5X ULN	>2.5 - 5.0 X ULN	>5.0 - 20.0 x ULN	>20.0 X ULN
Bilirubin	WNL	>ULN - 1.5 X ULN	>1.5 - 3.0 x ULN	>3.0 - 10.0 x ULN	>10 x ULN
Hypoalbuminemia	WNL	<LLN - 3 g/dL	$\geq 2$ - <3 g/dL	<2 g/dL	-
Prothrombin time (PT)	WNL	>ULN - 1.5 x ULN	>1.5 - 2 x ULN	>2 x ULN	
Liver dysfunction/failure (clinical)	normal	-	-	asterixis	Encephalopathy or coma
Hypokalemia	WNL	<LLN - 3.0 mmol/L	-	2.5 - <3.0 mmol/L	<2.5 mmol/L
Hypophosphatemia	WNL	<LLN -2.5 mg/dL <LLN - 0.8 mmol/L	2.0 - <2.5 mg/dL 0.6 - <0.8 mmol/L	1.0 - <2.0 mg/dL 0.3 - <0.6 mmol/L	<1.0 mg/dL <0.3 mmol/L
Creatinine	WNL	>.5 above baseline	>1.5 - 3.0 x ULN	>3.0 - 6.0 x ULN	>6.0 x ULN
Bicarbonate	WNL	<LLN - 16 mEq/dL	11 - 15 mEq/dL	8 - 10 mEq/dL	<8 mEq/dL
CPK (creatinine phosphokinase)	WNL	>ULN - 2.5 x ULN	>2.5 - 5 x ULN	>5 - 10 x ULN	>10 x ULN
Amylase	WNL	>ULN - 1.5	>1.5 - 2.0 x	>2.0 - 5.0 x	>5.0 x ULN

		x ULN	ULN	ULN	
Lipase	WNL	>ULN - 1.5 x ULN	>1.5 - 2.0 x ULN	>2.0 - 5.0 x ULN	>5.0 x ULN
Sinus bradycardia	None	asymptomatic, not requiring treatment	symptomatic, but not requiring treatment	symptomatic and requiring treatment	life-threatening (e.g., arrhythmia associated with CHF, hypotension, syncope, shock)
Sinus tachycardia	None	asymptomatic, not requiring treatment	symptomatic, but not requiring treatment	symptomatic and requiring treatment of underlying cause	-
Conduction abnormality Atrio-ventricular heart block	None	Asymptomatic, not requiring treatment (e.g. Mobitz type I second-degree AV block, Wenkebach)	Symptomatic, but not requiring treatment	Symptomatic and requiring treatment (e.g. Mobitz type II second degree AV block, third degree AV block)	Life-threatening (e.g. arrhythmia associated with CHF, hypotension, syncope, shock)
Supraventricular arrhythmias (SVT/atrial fibrillation/flutter)	None	asymptomatic, not requiring treatment	symptomatic, but not requiring treatment	symptomatic and requiring treatment	life-threatening (e.g., arrhythmia associated with CHF, hypotension, syncope, shock)
Cardiac-ischemia/infarction	None	non-specific T-wave flattening or changes	asymptomatic, ST- and T-wave changes suggesting ischemia	angina without evidence of infarction	acute myocardial infarction

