#### A1. Inclusion criteria: Primary Study (nucleoside analogue-naïve subjects)

- 1) Age >18 years and older, male or female
- 2) Known serum HBsAg positivity for 24 weeks
- 3) Detectable HBV DNA > $10^4$  IU/ml. For patients with cirrhosis HBV DNA > $10^3$  IU/ml
- 4) Serum ALT or AST levels 1.5 X ULN (for ALT:  $\geq 62$  U/L and for AST:  $\geq 46$  U/L) based on at least two determinations taken at least one month apart during the 24 weeks before study entry; no ALT requirement for patients with cirrhosis
- 5) Liver biopsy within 2 years of entry that is consistent with chronic hepatitis and with a histology activity index (HAI) score of 4 or more (scores range from 0-18) and an Ishak fibrosis score of at least 1 (scores range from 0-6). For patients who have had a liver biopsy at another institution, slides must be obtained for reading and scoring at the NIH.
- 6) Written informed consent

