#### A2. Inclusion criteria: Salvage Study (nucleoside analogue experienced subjects)

- 1) Age >18 years and older, male or female
- 2) Known serum HBsAg positivity for 6 months

- 3) Detectable **HBV DNA >10^2** IU/ml.
- 4) Liver biopsy within 5 years of entry that is consistent with chronic hepatitis
- 5) Written informed consent

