Patients will be seen in the outpatient clinic at weeks 0, 2, 4, 8, 12, 24, 36, and 48 weeks during the first year of therapy and at 12 week intervals thereafter.

At 48 weeks, all patients will be readmitted to the NIH Clinical Center and undergo a repeat thorough medical evaluation and liver biopsy. Patients in the salvage arm will be excluded from undergoing the 48 week liver biopsy. Continuation of therapy thereafter will depend upon both tolerance and benefit. All patients will undergo a 192 week follow-up biopsy to assess long-term efficacy and durability of response. Benefit is described in Section F “Assessment of Response” and tolerance in Section G “Assessment of Toxicity.”

The side effects will be monitored regularly. Tenofovir and emtricitabine will be stopped if moderate side effects attributable to either or both medications develop and persist for at least one week or on repeat testing. The medication(s) can be restarted if the adverse event resolves and does not appear to be related to either or both medications.

In the absence of toxicity attributable to either agent, combination therapy with tenofovir and emtricitabine or monotherapy with tenofovir will be continued for 192 weeks. Study medication/s will be discontinued if there is serological evidence of resolution of chronic hepatitis B, as shown by loss of HBsAg, documented on two serum samples taken at least six months apart.

Patients on therapy who develop evidence of drug resistance with elevations of serum aminotransferase levels twice above normal and HBV-DNA levels greater than  $10^6$  IU/ml will be switched to alternative therapies if mutually agreed between the patient and the investigators.

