#### **F. Assessment of response:**

In this study, the combination of tenofovir and emtricitabine and tenofovir monotherapy will be evaluated for long-term effects on chronic hepatitis B in both HBeAg-positive and -negative cohorts and in treatment naïve and those with resistance to lamivudine, adefovir, entecavir or all agents.

Definitions:

- a) **Full virological response:** absence of detectable HBV DNA by PCR ( $<10^2$  IU/ml)
- b) **Partial virological response:** suppression of HBV DNA to  $<10^4$  IU/ml but  $>10^2$  IU/ml
- c) **Serological response (HBeAg-positive patients only):** loss of detectable HBeAg.
- d) **Full biochemical response:** fall of serum ALT into the normal range ( $<41$  IU/L)
- e) **Partial histological response:** improvement in liver histology as defined by a decrease in the inflammatory component of the histological activity index (HAI) score by 3 points or more and no worsening of the Ishak fibrosis score. Histological responses will be assessed after 48 and 192 weeks of therapy.
- f) **Complete histological response:** improvement in liver histology as defined by a decrease in the inflammatory component of the histological activity index (HAI) score by 3 points or more and no worsening of the Ishak fibrosis score and a decrease of the HAI score to 3 or less. Histological responses will be assessed after 48 and 192 weeks of therapy.
- g) **Combined response:** the combination of a virological, serological, biochemical and histological response.
- h) **Complete Response:** Loss of HBsAg. A complete response is the major focus and most hoped for outcome of long-term antiviral treatment of hepatitis B. A complete response is reason for stopping all antiviral treatment.

Beneficial responses are also characterized as initial, maintained or sustained:

- a) **Initial response:** full virological or biochemical response occurring within the first 24 weeks of therapy.

- b) **Maintained response:** virological, serological, biochemical, histological, or combined response present at the time of last observation in a patient still receiving therapy.
- c) **Sustained response:** virological, serological, biochemical, histological or combined response present at the time of last observation and at least six months after stopping therapy.

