Emtricitabine carries a black box warning advising of lactic acidosis and severe hepatomegaly with steatosis including death associated with its use.

Emtricitabine was evaluated in a randomized placebo controlled trial in 167 patients with chronic hepatitis B. The incidence of clinical adverse events during treatment was similar in the 2 groups. Severe (grade 3 or 4) adverse events were reported in 14 (8%) of 167 emtricitabine-treated patients and 7 of 81 patients given placebo (9%), and serious adverse events occurred in 8% (n = 13) and 9% (n = 7), respectively. Related serious adverse events were rare, 4 (2%) of 167 emtricitabine and 3 (4%) of 81 placebo patients. During treatment, the incidence of grade 3 or 4 laboratory abnormalities was significantly reduced in the emtricitabine group, 31 (19%) of 167 patients vs. 33 (41%) of 81 in the placebo group (P<.001), which was due to the lower incidence of grade 3 or 4 transaminase, ALT (7% emtricitabine [n = 11], 26% placebo [n = 21]) and aspartate aminotransferase (2% emtricitabine [n = 3], 12% placebo [n = 10]) (P $\leq$ .001).

Post treatment follow-up safety data were available from 145 patients in the emtricitabine group (median follow-up, 110 days) and 63 patients in the placebo group. Post treatment exacerbation of CHB developed in 33 patients (23%) who had received emtricitabine and 3 placebo patients (5%) (P = .001), with a median time to onset of 10 weeks following the end of treatment (interquartile range, 8-16 weeks). One patient randomized to emtricitabine with marked bridging fibrosis at entry developed severe icteric post treatment exacerbation of CHB and required liver transplantation. All other patients recovered without clinical complications (overall, 14 with and 19 without antiviral therapy).

Long-term carcinogenicity studies of emtricitabine in rats and mice are in progress. Emtricitabine was not toxic in the reverse bacterial test (Ames test), mouse lymphoma or mouse micronucleus assays.

Emtricitabine did not affect fertility in male rats at approximately 140-fold or in male and female mice at approximately 60-fold higher exposures than in humans given the recommended 200 mg dose. Fertility was normal in the offspring of mice exposed daily from before birth (in utero) through sexual maturity at daily exposures of approximately 60-fold higher exposures than in humans given the recommended 200 mg dose.

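### Appendix B grades ALT and AST only against ULN, although most naive patients and all relapsers must qualify with one of them raised, so grades tabulated by arm would mix entry disease and disease control with on-drug worsening

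*Combined protocol and SAP*

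**What the plan says.** **Grading.** Table 1 of Appendix B puts ALT ("SGPT (ALT) (serum glutamic pyruvic transaminase") and AST on one scale: Grade 0 within normal limits, Grade 1 above ULN to 2.5 x, Grade 2 above 2.5 to 5 x, Grade 3 above 5 to 20 x, Grade 4 above 20 x ULN. Other rows of the table do look back to the patient's own starting point: Grade 1 diarrhea is counted over the pre-treatment stool frequency, Grade 1 fatigue over baseline, and Grade 1 creatinine is ">.5 above baseline".

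**Entry.** Section A1 (naive patients) requires "Serum ALT or AST levels 1.5 X ULN", given as ALT of at least 62 or AST of at least 46 U/L on two determinations, with "no ALT requirement for patients with cirrhosis". Section A.3 (relapsers) sets the same thresholds without the cirrhosis exemption. Section A2 (other treatment-experienced patients) has no enzyme criterion. No section sets an upper enzyme limit.

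**Use.** The Précis makes relative safety of the two regimens a study aim. Section F defines full biochemical response as "fall of serum ALT into the normal range", below 41 IU/L. Section I specifies no safety analysis, and no section defines a treatment-emergent laboratory change or an ALT flare.

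**The concern.** The enzyme that eligibility requires to be abnormal is graded as if every patient began at normal. A table of worst ALT or AST grade by arm would then have three ingredients that cannot be separated: how active the disease was at entry, how quickly treatment brought it down, and whether anything got worse on drug. Only the third is a safety finding. The second is close to an efficacy result, since moving to ALT Grade 0 is essentially the biochemical response of Section F.

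At stake is what the trial can say about comparative hepatic safety. Section I powers the trial on 94% against 70% full virological response, so a difference in disease control between arms is part of the planning assumption. If it occurs, the better-suppressed arm could show lower liver-enzyme grades without the drugs differing in hepatotoxicity.

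**Working it through.** **1. The plan's own threshold.** With the ALT normal limit of 41 from Section F, 1.5 x 41 = 61.5, which rounds to the stated 62 U/L. It reproduces. For AST, 46 / 1.5 = 30.7, an implied ULN of about 31; the protocol does not state the AST limit.

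**2. Entry values on the Appendix B scale.** The lowest qualifying ALT is 62 / 41 = 1.51 x ULN, inside Grade 1. Grade 2 starts above 2.5 x 41 = 102.5 U/L and Grade 3 above 5 x 41 = 205 U/L. With no upper entry limit, those grades too are open to a patient before dosing.

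**3. How many places.** The group ceilings in Section D give 20 (A) + 20 (B) + 20 (E) = 60 of 100. This agrees with the Protocol section's at least 40 naive patients and up to 20 relapsers. (A sentence in Section D gives other totals, at least 60 in A and B; it does not fit its own group ceilings and is not used here.) Naive cirrhotics must be subtracted. No cirrhosis share is given for this trial. The predecessor adefovir trial had 4 cirrhotics: 4/39 = 10% of those enrolled, or 4/31 = 13% of those with a year of therapy. Taking that range as an assumption, 40 x 0.87 to 40 x 0.90 is about 35 to 36 naive patients, plus 20 relapsers, so about 55 to 56 patients bound by the criterion.

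**4. What the grades show and miss (ALT, ULN 41, illustrative courses).**

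| Course, U/L | x ULN | Grade | Relative change |
|---|---|---|---|
| 62 to 98 | 1.51 to 2.39 | 1 to 1 | 98/62 = 1.58 x baseline |
| 209 to 418 | 5.1 to 10.2 | 3 to 3 | 2.0 x baseline |
| 107 to 213 | 2.6 to 5.2 | 2 to 3 | 2.0 x baseline |
| 62 to 30 | 1.51 to 0.73 | 1 to 0 | also a biochemical response |
| 62 to 30 to 95 | 1.51 to 0.73 to 2.32 | 1 to 0 to 1 | 95/62 = 1.53 x baseline; 95/30 = 3.17 x nadir |

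The first two rows are rises that leave the grade unchanged. The third shows that the scale does register many large rises. The last is a threefold rebound from nadir: the grade changes between visits (0 to 1), but the worst grade equals the entry grade. A rule that counted only grades above day 0 would not count it.

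**5. The protocol's cited example.** In the placebo-controlled emtricitabine trial of Section G, Grade 3 or 4 ALT occurred in 21/81 = 26% on placebo and 11/167 = 7% on drug. Section G says of the lower overall rate of laboratory abnormalities on drug, "which was due to the lower incidence of grade 3 or 4 transaminase". This shows that ALT grades can follow disease control. It does not measure how far they would do so here.

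**The case against.** The best reply is that little in the protocol turns on these grades. Section I compares no laboratory grades. Section D says study drugs "will be stopped if moderate side effects attributable to either or both medications develop" and persist, and names no ALT grade. Section M records adverse events at least possibly related to participation and exempts those explained by the natural history of hepatitis B, unless their rate or severity exceeds what is known. These provisions separate entry disease from drug toxicity for clinical action and reporting. All of that stands, and it limits the consequence to tabulation. It does not supply a baseline reference, and the rate-or-severity exception itself needs a way to tell worsening from entry disease.

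Four stronger readings are tempting but not supported:

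- *Every such patient is Grade 1 on day 0 by rule.* Qualifying values come from screening, up to 24 weeks before entry for naive patients and with no stated window for relapsers. One enzyme is enough, so neither ALT nor AST is individually guaranteed raised.
- *The trial counts entry ALT as toxicity, or would stop drug for it.* No text says so. Reading Section D's moderate side effects as ALT Grade 2 would ignore its requirement for attribution.
- *The 19-point gap (26% less 7%) is the expected distortion.* That was placebo against active drug. Here both arms receive tenofovir, and the first hypothesis for naive patients expects similar ALT patterns. Section G also does not say how those grades were referenced.
- *A stated share starts at Grade 2 or 3.* The documents give no entry ALT distribution; any share would rest on an invented one.

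**Conclusion.** The point holds for the summary and comparison of hepatic safety. Appendix B is the only enzyme scale the protocol offers, and it cannot by itself distinguish entry disease from worsening on treatment. Up to about 60 of 100 places are affected, or about 55 to 56 if the predecessor trial's cirrhosis share applies. Most of these patients will be at Grade 1 or higher in at least one enzyme before dosing, on the assumption that screening values broadly persist to day 0.

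The size of any between-arm distortion cannot be derived from the documents. With two active arms it is probably smaller than a placebo comparison would suggest. The primary endpoint, power calculation and stopping rules are untouched. The change is still worth making because relative safety is a stated aim and the remedy is nearly free.

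**What to change.** Keep the Appendix B grades and add a footnote stating that ALT, AST and any other row abnormal at entry (for example bilirubin or platelets in cirrhotics) will be summarised by arm in two ways:

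1. A shift table from day-0 grade to worst on-treatment grade.
2. Rises in ALT and AST as multiples of baseline and, separately, of the on-treatment nadir.

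Do not make one grade above day 0 the sole counting rule: it misses rises within a grade and rebounds from nadir back to the entry grade. Section I should refer to the footnote and state that some mixing with efficacy will remain, because an arm with better suppression may also have fewer disease flares.

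The cost is one footnote, a cross-reference and some extra tabulation. Section E already draws the chemistry panel at every visit, so no new data are needed. This concerns analysis only and changes no clinical rule.
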